### 9.1.2 Secondary Outcomes

#### 9.1.2.1. Objective Response (OR)

Best overall response is the best response recorded over the whole period of assessment and could be complete response (CR), partial response (PR), stable disease (SD), progressive disease (PD) or inevaluable for response (NA, for which reasons such as early death due to disease or early death due to toxicity will be specified). Objective Response (OR) is the occurrence of CR or PR as best overall response. Objective Response will be based on responses confirmed using the subsequent 9-weekly scan but objective response based on unconfirmed responses will also be reported.

Furthermore, the number (and %) of patients in each best response category will be reported.

#### 9.1.2.2. Health Related Quality of Life (HRQoL)

The purpose of HR QoL measurement is to quantify the degree to which the medical condition or its treatment impacts the individual's life in a valid and reproducible way. Health-related quality-of-life will be measured using the FACT-L and EQ-5D questionnaires, and a patient-generated subjective global assessment questionnaire, as identified in the protocol (see protocol appendix for questionnaires). The FACT-L questionnaire generates 5 measures for analysis: physical well-being, social/family well-being, emotional well-being, functional well-being and the lung cancer subscale. The EQ5D questionnaire generates 2 measures for analysis: an EQ5D utility measure and an EQ5D Visual Analogue Scale. Questionnaires will be administered on day 1 of every cycle prior to receiving treatment and also at the end of treatment visit.

#### 9.1.2.3. Time to Progression (TTP)

This is defined as the time from commencement of trial treatment to the date of CT scan when progressive disease is first recorded. Patients with no recorded progression at the time of analysis or who die without recorded progression will be censored at the date of the CT scan when they were last recorded with an evaluable measure that was not progression.

---

#### 9.1.2.4. Progression-Free Survival Time (PFS)

This is defined as the time from commencement of trial treatment to the date of CT scan when progressive disease first recorded or date of death without previously recorded progression. Patients who are alive with no recorded progression at the time of analysis will be censored at the date of the CT scan when they were last recorded with an evaluable measure that was not progression.

#### 9.1.2.5. Overall Survival Time (OS)

This is defined as the time from commencement of trial treatment to the date of death. Patients who are alive at the time of analysis will be censored at the date last confirmed alive.

#### 9.1.2.6. Duration of Objective Response (DOR) and Duration of Stable Disease (DSD)

Duration of objective response and duration of stable disease are defined as the time from commencement of trial treatment to the date of the subsequent CT scan when progressive disease is first confirmed or date of death without previously recorded progression. This outcome is calculated and reported separately for patients who achieve an OR or SD. Patients experiencing OR or SD who are alive with no recorded progression at the time of analysis will be censored at the date of the CT scan when they were last recorded with an evaluable measure that was not progression.

These outcomes are effectively a subgroup analysis of PFS using categories that reflect those patients whose best response is SD (DSD) and those patients who achieve an OR (DOR). Patients may belong to one analysis but not both. Patients who record no RECIST data or whose best response is PD will not be used in this analysis.

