**Document Control Sheet**

Statistical Analysis Plan version & date:	Reason for update:	To match protocol version & date:
0.1, 12-Sep-2016	Initial creation	2.0a, 07-Jun-2016
0.2, 19-Oct-2016	Revision after LB comments	2.0a, 07-Jun-2016
1.0, 19-Oct-2016	Initial release	2.0a, 07-Jun-2016
2.0, 18-May-2017	Created "Rules of Inference" section. Refined outcome definition in protocol and SAP.	4.0
3.0, 10-Apr-2018	
Clarified intention to publish primary outcomes before the longer term secondary outcomes.
 
Clarified that the co-primary DCB outcome is treated as success if: CR or PR or SD is measured at or after the second scheduled CT scan; and the scan date is at least 16 weeks from registration. The second scan is scheduled at 18 weeks but frequently these are conducted slightly early for reasons outside the control of the trials unit. The third scheduled scan is not until 27 weeks.
 
Clarified that PD-L1 scores expressed as a range are interpreted as the midpoint, e.g. 10-20% is interpreted as PD-L1 = 15%.
 
Added hierarchical model as a proposed supplementary method of analysing primary outcomes. The described BEBOP method requires that baseline covariates be present. This assumption became pertinent when we allowed PD-L1-assay failures to register. The hierarchical
	5.0, 14-Aug-2017

	
method does not mandate covariates be present.
 
Added spider plot to specified graphical methods.
	
4.0, 18-Jun-2018	
Clarified the analysis method for DOR and DSD, and minor typographical changes.
	6.0
5.0, 31-Jan-2019	
Added prose describing the prior predictive event distributions of DCB and toxicity.
 
Removed the proposal of a hierarchical analysis. This was proposed to include patients with missing covariate data, because “missing” could be included as another variable level whilst providing some shrinkage to avoid overfitting the relatively small group. However, the inherent exchangeability assumption is not appropriate. We added instead a method that will use the original proposed BEBOP model and multiply-impute missing covariates.
 
Added plans to impute sum of target lesions when it is not reported but a RECIST response with respect to target lesions is reported, and vice versa.
 
Clarified some minor points.
 
Updated storage locations of snapshots, analyses, etc.
	6.0, 10-Jul-2018

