## DCB

Patients are scheduled to have CT scans every 9 weeks from baseline until disease progression. On each occasion, overall tumour burden will be assessed using RECIST 1.1, according to the study protocol. DCB is defined as the occurrence of CR, PR or SD without prior PD at or after the second scheduled CT scan. The second scan is scheduled to occur at the end of treatment cycle 6 at 18 weeks. For many reasons, scans often do not take place on the desired date. The exact timing of scans is largely out of the control of the trials office. The third scheduled scan is at 27 weeks. In NSCLC, disease status could easily change during the intervening 9 weeks. When calculating DCB, we include scans that occurred at least 16 weeks after registration.

For example, a disease response of (CR / PR / SD) at the first scheduled scan at 9 weeks, followed by a disease response of (CR / PR / SD) at the second scheduled scan at 16+ weeks would constitute DCB. Likewise, (CR / PR / SD) at 9 weeks, missing data at 18 weeks, and (CR / PR / SD) at the third scheduled scan at 27 weeks would also constitute DCB.

Patients for whom the DCB outcome could not be determined will be taken to be non-responders.

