### 9.2.3 Secondary Outcomes

#### 9.2.3.1. Time-to-event outcomes

Time-to-event outcomes (TTP, PFS, OS, DOR, DSD) will be analysed using the Kaplan-Meier method. Median time-to-event (and 90% CIs) will be presented for each outcome. Milestone events rates will be presented (with 90% CIs) for each outcome. Milestone rates will be presented at appropriate times, selecting from 3, 6, 12, 18 and 24 months. Note that 90% confidence intervals are appropriate in this single arm phase II trial. These analyses will use the analysis population; the DoR analysis will use the subset that achieve partial or complete RECIST response.

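### Duration of objective response is timed from the start of treatment, so the reported figure is PFS among responders and includes event-free time before the response

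*SAP*

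**What the plan says.** SAP 9.1.2.6 gives one definition for both duration outcomes: "Duration of objective response and duration of stable disease are defined as the time from commencement of trial treatment", ending at progression or death. Protocol 2.2.2.6 and 13.1.2.6 agree with it. PFS in SAP 9.1.2.4 has the same starting point ("This is defined as the time from commencement of trial treatment to the date of CT scan when progressive disease first recorded", or death) and the same censoring rule. The SAP is open about the consequence: "These outcomes are effectively a subgroup analysis of PFS using categories that reflect those patients whose best response is SD", with DOR being the matching group of patients who achieve an objective response.

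Membership of that group depends on later scans: "Objective Response will be based on responses confirmed using the subsequent 9-weekly scan". SAP 9.2.3.1 says that "the DoR analysis will use the subset that achieve partial or complete RECIST response". It plans a Kaplan-Meier median with a 90% CI for DOR, and "Milestone rates will be presented at appropriate times, selecting from 3, 6, 12, 18 and 24 months". Neither document times DOR from the first CR or PR.

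**The concern.** DOR is listed as a secondary outcome separate from PFS and should answer a separate question: once a response is seen, how long does it last? With the clock started at first dose it does not answer that. The reported median and milestone rates are longer or higher than time in response, because each responder brings along the time before the response.

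Durability is part of the trial's rationale. Protocol 1.1.2 cites a median duration of response of 12.5 months from an earlier pembrolizumab study (23.3 months first line). A PePS2 figure under the same name is likely to be read beside it. The documents do not say how the 12.5 months was timed, so the two may or may not share a starting point. Either way, the PePS2 figure overstates time in response.

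Duration of stable disease is not in dispute. Stable disease has no later onset date, so the start of treatment is a reasonable origin.

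**Working it through.** **Inputs from the documents.** Scans every 9 weeks; 21-day cycles; "The second scan is scheduled to occur at the end of treatment cycle 6 at 18 weeks"; confirmation at the next 9-weekly scan; milestones chosen from 3, 6, 12, 18 and 24 months.

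**The plan's own figure.** 6 cycles × 21 days = 126 days = 18 weeks, and 2 × 9 weeks = 18 weeks. The stated time of scan 2 is reproduced.

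**Added time per responder.** This equals the time from first dose to the first scan showing response. Months = weeks × 7 / (365.25/12):

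| First response seen at | Weeks | Months added |
|---|---|---|
| Scan 1 | 9 | 2.07 |
| Scan 2 | 18 | 4.14 |
| Scan 3 | 27 | 6.21 |

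The interval is event-free because Protocol Appendix 2 counts best response only up to progression, and a patient who dies first cannot enter the group.

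**Early scans.** The SAP's Document Control Sheet notes: "The second scan is scheduled at 18 weeks but frequently these are conducted slightly early". Table 1 as extracted appears to mark imaging in the week 6 and week 15 columns, with results due before cycles 4 and 7. On that reading the added time is 1.38 months (scan 1) or 3.45 months (scan 2). If the 9 weeks run from a baseline scan taken 28 days before treatment, scans 1 and 2 fall at weeks 5 and 14, giving 1.15 and 3.22 months. The added time is positive in every case.

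**Illustration of the effect on the summaries.** The following assumptions are not in the documents. First response is at scan 1 in 60, 80 or 100% of responders and at scan 2 in the rest. True progression after response is exponential with median 6, 12 or 18 months. Death without progression has median 60 months. Progression is recorded at the next scan. Only confirmed responders are kept. With 400,000 simulated responders per setting, the ranges over the nine settings are:

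| Scan timing | Mean added time (months) | 6-month rate, excess (points) | 12-month rate, excess (points) |
|---|---|---|---|
| On schedule | 2.1–2.9 | 10–24 | 7–16 |
| Every scan 1 week early | 1.8–2.7 | 2–11 | 7–16 |
| Every scan 2 weeks early | 1.6–2.4 | 1–11 | 1–5 |
| Weeks 6, 15, and so on | 1.4–2.2 | 1–11 | 1–5 |

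Excess means the rate timed from first dose minus the rate timed from first response. On schedule the 6-month rates are 98–99% against 75–88%.

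The excess depends on the scan grid. Week 27 is 6.21 months and week 26 is 5.98, so a one-week shift moves scan 3 across the 6-month mark. Week 53 is 12.19 months and week 52 is 11.96, so a two-week shift moves scan 6 across the 12-month mark. The mean added time is therefore the steadier measure. In these settings the median from first dose exceeded the median from response by at least 2.07 months on schedule, 1.6 months two weeks early, and 1.4 months on the week 6/15 timetable.

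**Three-month milestone.** A response first seen at scan 1 and confirmed at scan 2 implies no event before week 18 (4.1 months). The 3-month rate from first dose is therefore 100% by construction. Timed from first response it is still about 99%, because confirmation needs a further 9 weeks.

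**Scale.** 2.07/12.5 = 17% and 2.90/12.5 = 23% of the median cited in Protocol 1.1.2.

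**The case against.** The strongest reply is that nothing here is inconsistent or hidden. The three definitions agree, SAP version 4.0 clarified this analysis, and the text says outright that it is PFS in a subgroup. An analyst cannot misapply it, and one line in the report could tell readers how DOR was timed. The swimmer plot in SAP 9.2.2.2 would show durability patient by patient.

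The size can also be questioned. Only the scan timetable comes from the documents, and earlier scanning brings the mean added time down to 1.4–2.2 months. The large 6-month contrast appears only when every scan is exactly on schedule. No comparison with the 12.5 months is planned. The outcome is descriptive and will be imprecise: if 19.4% of 60 patients respond (the overall rate cited in Protocol 1.1.2), there are about 12 responders. With an assumed exponential true median of 12 months and no censoring, a median from 12 patients ranges from about 6 to 22 months (5th to 95th percentile).

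Much of this stands. It is a mismatch between label and quantity, not a contradiction, and the milestone contrasts should not be used as headline evidence. But disclosure in the SAP does not change the number published as DOR, and the swimmer plot is optional and gives no estimate. Imprecision does not excuse a shift that always goes in the same direction.

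**Conclusion.** The point holds. What the plan will report as DOR is PFS among responders, longer than time in response by the time to the first response scan: nominally 2.1 months at scan 1 and 4.1 at scan 2. The mean excess is 2.1–2.9 months on schedule and 1.4–2.2 months on the earliest timetable simulated, if 60–100% of responders are first seen at scan 1. The direction does not depend on that assumption; the size does. The definition should be changed, though the consequence is limited to one descriptive secondary outcome.

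**What to change.** In Protocol 2.2.2.6 and 13.1.2.6 and SAP 9.1.2.6, define DOR as the time from the first CT recording the CR or PR (later confirmed) to first recorded progression or death, censored as for PFS. Leave duration of stable disease timed from the start of treatment. If the present quantity is still wanted, report it alongside as *PFS in responders*.

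Three editorial points can go in with the same change:

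- Add the word confirmed to the DOR population in SAP 9.2.3.1, to match SAP 9.1.2.1.
- Align the endpoint wording. The duration outcomes end at progression first confirmed and PFS at progression first recorded, and no rule for confirming progression is given.
- Do not select the 3-month milestone for DOR.

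No extra patients, visits or scans are needed, since the dates are already collected. The costs are an amendment to a prespecified secondary outcome in an open-label trial, which should be dated and explained; the loss of a common time origin for DOR, duration of stable disease and PFS; and a reported median DOR shorter by roughly 2 months or somewhat more.

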## 9.2 Methods of Analysis

### 9.2.1 Stratification variables

Each patient will have a PD-L1 proportion score. Where a range of PD-L1 proportion scores is specified for a tumour sample (e.g. 10-20%), the PD-L1 proportion score for that patient will be taken to be the mid-point (e.g. 15%).

### 9.2.2 Primary Outcomes

The co-primary outcomes will be summarised as toxicity rate and disease control (frequently referred to simply as *efficacy* in this section) rate and analysed simultaneously using the BEBOP (Bayesian Evaluation of Binary Outcomes with Predictive variables) method, developed by Brock, *et al.* (publication in draft).

Each patient will have a PD-L1 proportion score and this will determine membership to one of three PD-L1 categories, shown in Table 1. These categories were validated to be predictive of response in Garon, *et al* [1]. Additionally, each patient will be either previously treated or not previously treated. These two variables yield the six PePS2 cohorts shown in Table 2.

**Table 1 – A patient's PD-L1 category is inferred from their PD-L1 proportion score**

Criteria on PD-L1 proportion score $z$	PD-L1 category
$z < 1\%$	Low
$1\% \leq z < 50\%$	Medium
$z \geq 50\%$	High

**Table 2 – PePS2 cohorts and corresponding vectors of predictive values,  $x_i = (x_{1i}, x_{2i}, x_{3i})$** 

Cohort	Treatment status	PD-L1 category	$x_{1i}$	$x_{2i}$	$x_{3i}$
1	Not pre-treated	Low	0	1	0
2	Not pre-treated	Medium	0	0	1
3	Not pre-treated	High	0	0	0
4	Pre-treated	Low	1	1	0
5	Pre-treated	Medium	1	0	1
6	Pre-treated	High	1	0	0

Let  $\theta = (\alpha, \beta, \gamma, \zeta, \lambda, \psi)$  be a vector of parameters. We model the marginal probability of efficacy in patients with the predictive values  $\mathbf{x} = (x_1, x_2, x_3)$  using the logit-model

$$\pi_E(\mathbf{x}, \theta) = \alpha + \beta x_1 + \gamma x_2 + \zeta x_3$$

and the marginal probability of toxicity using the logit-model

$$\pi_T(\mathbf{x}, \theta) = \lambda$$

Using these formulae, the probability of efficacy is different for each cohort. In contrast, the probability of toxicity is uniform across the cohorts. These assumptions are supported by data published on similar studies in performance status 0 & 1 patients [1, 2].

Let  $a=1$  for a given patient if they experience efficacy, and  $b=1$  if they experience toxicity, else 0. The joint probability density of efficacy and toxicity events for this patient is modelled using the formula

$$\pi_{a,b} = \pi_E^a (1 - \pi_E)^{1-a} \pi_T^b (1 - \pi_T)^{1-b} + (-1)^{a+b} \pi_E (1 - \pi_E) \pi_T (1 - \pi_T) \frac{e^\psi - 1}{e^\psi + 1}$$

The fraction on the right-hand side, which ranges in value over (-1, 1) for  $\psi \in (\infty, -\infty)$ , models the association between efficacy and toxicity events.

Let  $\mathbf{X} = \{(\mathbf{x}_1, a_1, b_1), \dots, (\mathbf{x}_n, a_n, b_n)\}$  be the trial outcomes for  $n$  patients. The aggregate likelihood function is

$$L(\mathbf{X}, \theta) = \prod_{i=1}^n \pi_{a_i, b_i}(\mathbf{x}_i, \theta)$$

With prior  $f(\theta)$ , the posterior distribution, up to proportionality, is

$$f(\theta | \mathbf{X}) \propto f(\theta) L(\mathbf{X}, \theta)$$

We use normal prior distributions for the elements of  $\theta$  with means and variances given in Table 3. These give prior events rates of approximately 20% for efficacy and toxicity in each cohort. This can be verified by setting  $\mathbf{X} = \{ \}$  and estimating the 'posterior' probabilities of efficacy and toxicity. The prior event rates we use represent conservative extrapolations of those published in performance

status 0 & 1 patients [1, 2], where, if we were to anticipate a difference compared to our performance status 2 population, the stronger PS0/PS1 patients would be more likely to achieve response and less likely to experience toxicity.

**Table 3 – Parameters for normal prior distributions for the elements of  $\theta$**

Parameter	Mean	Variance
$\alpha$	-2.2	4
$\beta$	-0.5	4
$\gamma$	-0.5	4
$\zeta$	-0.5	4
$\lambda$	-2.2	4
$\psi$	0	1

These priors generate prior predictive efficacy and toxicity outcomes shown in Figure 1. We see that modest event rates for each outcome in each cohort are anticipated, but that high event rates are possible in each case. In this regard, our priors can be regarded as having a regularising effect. The prior expected event rates with credible intervals are shown in Table 4. The expected event rates are approximately 20%, although materially lower and greater rates are facilitated in each cohort.

**Table 4 - Credible intervals for events rates drawn from the prior predictive distribution of the regularising priors in Table 3. Eff and Tox show the probability of efficacy and toxicity, respectively. Lowercase l and u show the central 50% credible interval and upper-case L and U show the central 90% credible interval.**

Previous	PD-L1	EffL	Effl	Eff	Effu	EffU
TN	Low	0.00	0.01	0.21	0.31	0.87
TN	Med	0.00	0.01	0.21	0.31	0.87
TN	High	0.00	0.03	0.20	0.30	0.75
PT	Low	0.00	0.00	0.21	0.30	0.92
PT	Med	0.00	0.00	0.21	0.30	0.92
PT	High	0.00	0.01	0.21	0.32	0.87
		ToxL	Toxl	Tox	Toxu	ToxU
TN / PT	Low-High	0.00	0.03	0.20	0.30	0.75

In a manuscript presently under review, we compared the operating performance under these priors to diffuse priors (i.e. greater prior variances) and informative priors (i.e. anticipating increasing efficacy in PD-L1). We demonstrated that informative priors coerced undesirable bias, and diffuse priors generate implausible prior predictive outcome rates with the majority of probability mass close to 0 or 1, offer poor posterior coverage and yield large empiric standard errors. We concluded that our regularising priors offer an attractive balance.

[figure not shown]

Figure 1 - Prior predictive distributions of the probabilities of efficacy and toxicity in all cohorts.

Given trial data  $\mathbf{X}$ , inferences on  $\theta$  and functions of  $\theta$ , such as  $\pi_E(\mathbf{x}, \theta)$  and  $\pi_T(\mathbf{x}, \theta)$ , are made using the posterior predictive distributions.

If a patient does not report any adverse event that satisfies the criteria to be a toxicity event, that patient will be treated as not having had toxicity. If a patient does not report CT scans that satisfy the criteria to be a DCB event, that patient will be treated as not having had efficacy.

### 9.2.2.1. Missing data

The method described above requires covariate data be present. If a modest amount of covariate data is missing, we propose to:

- 1) Impute each possible combination of the missing covariates; this will yield  $1, \dots, M$  distinct complete datasets, each containing a small amount of imputed information;
- 2) Fit the model described above to each complete dataset to yield  $M$  sets of posterior samples;

---

3) Re-sample from the  $M$  sets of posterior samples with probabilities  $p_1, \dots, p_M$  determined by the likelihood of the imputed covariate vector, implied by the frequency of covariates in the fully-specified cases.

An example will be expository. Let us assume that two patients have missing PD-L1 status. We know that the PD-L1 category for each may be Low, Medium, or High, yielding  $3^2 = 9$  possible covariate imputations. We supplement the observed covariate data with the imputed data to generate 9 complete sets. The efficacy and toxicity outcomes are known in each instance. Fitting the model to each complete dataset, we obtain 9 sets of posterior samples of the estimated probabilities of efficacy and toxicity in the six cohorts. Let us also assume that the incidence of Low / Medium / High PD-L1 in the set of patients that report PD-L1 categories is 10% / 30% / 60%. We attach scenario likelihood  $0.1 * 0.1 = 0.01$  to the imputation Low / Low; and likelihood  $0.3 * 0.6 = 0.18$  to the imputation Medium / High; etc. To obtain pooled posterior samples from the 9 distinct sets of posterior samples, we select from the datasets with probabilities implied by the scenario likelihoods, and then select with replacement and uniform probability from the posterior samples for that scenario.

We stress that this method has been proposed to impute required yet missing covariate data only. It will not be used to impute outcomes.

This method will allow us to use the intended analysis method to study the outcomes of all evaluable patients, irrespective the presence of covariate information.

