### **4 ELIGIBILITY**

#### **4.1 Inclusion Criteria**

- Patients must have completed all standard of care therapy that the treating oncologist deems appropriate. All lines of therapy will be allowed.
- Histologically confirmed NSCLC and, if possible, confirmed PD-L1 status. Patients with both PD-L1 positive and negative tumours are eligible. Patients who have had systemic therapy since the biopsy do not need to have a repeat biopsy.
  - If the PD-L1 status has already been obtained from a nationally recognised and MSD-approved laboratory, this will be acceptable and repeat PD-L1 staining will not be required.
  - If a patient has had a repeat biopsy for the sole purpose of PD-L1 staining for the PePS2 trial but the biopsy failed to yield sufficient cells for PD-L1 status, this patient will still be eligible to enter the PePS2 trial but will be categorised as PD-L1 non-evaluable.

- Patients must have a performance status of 2 on the ECOG Performance scale (Appendix 1) with no deterioration over the previous 2 weeks assessed by consenting physician.
  - Patients must be ambulatory and capable of all self-care but unable to carry out any work activities.
  - Patients must be up and about more than 50% of waking hours.
- Life expectancy >12 weeks.
- CT scan of chest and abdomen within 28 days of starting pembrolizumab demonstrating uni-dimensionally measurable disease as per RECIST version 1.1 (Appendix 2).
- Demonstrate adequate haematological function:
  - Platelet count  $\geq 100 \times 10^9 /L$
  - Neutrophils  $\geq 1.5 \times 10^9 /L$
  - Haemoglobin  $\geq 90 \text{ g/L}$
- Demonstrate adequate hepatic function:
  - Serum bilirubin  $\leq 1.5 \times$  upper limit of normal (ULN)
  - Serum transaminases  $\leq 2.5 \times$  ULN
- Demonstrate adequate renal function
  - Creatinine clearance  $< 1.5$  times ULN concurrent with creatinine clearance  $> 50 \text{ ml/min}$  (calculated by Cockcroft and Gault equation – see Appendix 3). If this is  $\leq 50 \text{ ml/min}$  then an isotopic Glomerular Filtration Rate (GFR) may be carried out and must be  $> 50 \text{ ml/min}$
- Age  $\geq 18$  years.
- Provision of signed and dated, written informed consent prior to any trial specific procedures, sampling and analyses.
- Patients must agree to the use of contraception as detailed in section 4.3.

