## **5.2.1 Screening Investigations**

### ***5.2.1.1 Histologically Confirmed PD-L1 status***

As part of the pre-screening registration process, PD-L1 testing may be carried out on an archival biopsy sample if available or a newly obtained biopsy, at a nationally recognised MSD-approved laboratory for PD-L1 staining. Repeat biopsies are not required if the PD-L1 status is already known (see section 5.1).

Biopsies taken for PePS2 may be obtained by Endobronchial ultrasound (EBUS) or Computer-Tomography (CT)-guided. Five slides fresh cut sections from Formaldehyde Fixed Paraffin Embedded (FFPE) tissue will be assessed by the site Pathologist for PD-L1 testing with >50% tumour content and at least 50 viable neoplastic cells overall. These slides will then be shipped to an MSD-approved laboratory for PD-L1 testing and the Trial Office will inform sites of successful staining. The PD-L1 status of the patient must be known for patient to be eligible for the trial. The only exception to this will be patients who have submitted to a repeat biopsy for the explicit purpose of ascertaining the PD-L1 status in the PePS2 trial and where PD-L1 staining has failed on that repeat biopsy.

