## 11. STATISTICAL SOFTWARE

We have implementations of our PePS2 BEBOP design written in Python and Stan [3]. The Python implementation solves posterior integrals directly using Monte Carlo integration. Stan is a Bayesian programming language. The Stan implementation uses No U-Turn Sampling to sample elements from the posterior distribution. The two methods agree on the six-parameter model presented. The Python method cannot realistically be used on problems with more than six parameters because of the non-linear increase in difficulty of directly calculating integrals of higher dimension (the *curse of dimensionality*). The Stan method was developed with the prospect of analysing models with more than six parameters.

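### The pooling weights for missing PD-L1 leave out the known efficacy outcome, so the estimated PD-L1 effect on efficacy is pulled towards zero (about 3% with two patients missing, about 9% if six were missing)

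*SAP*

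**What the plan says.** Protocol 5.2.1.1 states that "The PD-L1 status of the patient must be known for patient to be eligible for the trial", with one exception: a repeat biopsy taken for the trial on which staining failed. Protocol 4.1 says of such a case that "this patient will still be eligible to enter the PePS2 trial but will be categorised as PD-L1 non-evaluable". Some missing PD-L1 is therefore expected, although neither document gives a number.

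SAP 9.2.2.1 handles it as follows: "If a modest amount of covariate data is missing, we propose to" fill in each possible combination of the missing covariates, fit the model to each completed dataset, and resample from the resulting posteriors. The resampling probabilities are "determined by the likelihood of the imputed covariate vector, implied by the frequency of covariates in the fully-specified cases". The worked example has two patients missing and observed frequencies of 10%, 30% and 60% for Low, Medium and High. It gives Low/Low a weight of 0.01 and Medium/High a weight of 0.18. The example also says: "The efficacy and toxicity outcomes are known in each instance".

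On the efficacy model, SAP 9.2.2 says: "Using these formulae, the probability of efficacy is different for each cohort". The toxicity model has a single parameter and no PD-L1 term.

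**The concern.** The weights use only how common each PD-L1 category is. If PD-L1 predicts efficacy, a patient's known outcome is evidence about the missing category: a responder is more likely to be High than a non-responder is. Giving both the same probabilities mixes responders into the Low and Medium cohorts and non-responders into the High cohorts more than the model supports. This pulls gamma (Low versus High) and zeta (Medium versus High) towards zero.

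At stake is a co-primary analysis. The section is the stated route for keeping every evaluable patient in the intended model, and the cohort approval rule is defined on that model's posterior. SAP 9.4.3 also expects the primary analysis to show whether the PD-L1 categories are valid in PS2 patients, and this bias works against seeing that effect.

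**Working it through.** **The SAP's own figures.** 3² = 9 completions; Low/Low 0.1 × 0.1 = 0.01; Medium/High 0.3 × 0.6 = 0.18. All reproduce, and no outcome term enters.

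**The algebra.** Let rho_k be the category frequencies, f(theta) the prior, and L_m(theta) the likelihood of completed dataset m. A patient with missing PD-L1 contributes sum_k rho_k · pi_ab(x_k, theta). Multiplying out over the missing patients gives

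posterior ∝ sum_m f_m · f(theta) · L_m(theta) = sum_m f_m · Z_m · (posterior from dataset m),

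where f_m is the product of the frequencies and Z_m = ∫ f(theta) L_m(theta) dtheta. The correct weight is f_m·Z_m, renormalised. The SAP uses f_m, which is right only if Z_m is the same for every completion.

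**Size in the worked example.** Take one untreated responder and one untreated non-responder, with the Scenario 8 untreated rates from SAP Table 6 (Low 0.167, Medium 0.192, High 0.500) treated as known.

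- Responder: total 0.1×0.167 + 0.3×0.192 + 0.6×0.500 = 0.3743. P(High) = 0.300/0.3743 = 0.80; P(Medium) = 0.0576/0.3743 = 0.15.
- Non-responder: total 1 − 0.3743 = 0.6257. P(High) = 0.300/0.6257 = 0.48; P(Medium) = 0.3×0.808/0.6257 = 0.39.
- Responder High with non-responder Medium: 0.8015 × 0.3874 = 0.31. The reverse: 0.1539 × 0.4795 = 0.07. The ratio is 4.2; the SAP gives both 0.18.

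With the untreated prevalences in SAP 9.3.2 (0.315, 0.436, 0.249), P(High) is 0.1245/0.2608 = 0.48 for a responder and 0.1245/0.7392 = 0.17 for a non-responder. Pooled frequencies give both (0.249 + 0.227)/2 = 0.24.

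**Simulation.** Inputs: 60 patients, SAP Table 3 priors, the SAP 9.3.2 Dirichlet for cohort membership, and Scenario 8 rates. PD-L1 was deleted completely at random in 2, 3, 6 or 9 patients (4,000, 3,000, 2,000 and 2,000 trials), with every distinct completion enumerated. The efficacy part of the model was fitted by importance sampling. At 10% true toxicity the toxicity rule passes with probability 0.999, so efficacy-only approvals are comparable with Table 6.

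Check with no PD-L1 missing, cohorts 1–6: approvals 44.9, 67.3, 98.0, 29.2, 50.2, 93.0%, against 45.7, 68.1, 97.9, 29.9, 49.3, 92.4% in Table 6.

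Attenuation under SAP weights, relative to outcome weights:

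| Missing | 2 | 3 | 6 | 9 |
|---|---|---|---|---|
| gamma | 2.9% | 4.4% | 8.7% | 13.0% |
| zeta | 2.6% | 3.7% | 7.3% | 11.4% |

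The shifts in posterior mean efficacy at 2 / 6 / 9 missing are −0.004 / −0.012 / −0.017 in cohort 3, −0.005 / −0.013 / −0.020 in cohort 6, +0.002 / +0.007 / +0.011 in cohort 1 and +0.002 / +0.005 / +0.008 in cohort 4. Posterior SDs are about 0.13 in the High cohorts and 0.07–0.09 in the Low cohorts.

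Approval (%), SAP weights v outcome weights:

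| Cohort (true rate) | 2 missing | 6 missing | 9 missing |
|---|---|---|---|
| 1 (16.7%) | 45.8 v 44.6 | 46.0 v 42.6 | 49.0 v 43.0 |
| 2 (19.2%) | 67.6 v 66.9 | 68.8 v 66.8 | 69.8 v 66.1 |
| 3 (50.0%) | 97.9 v 98.0 | 97.2 v 97.2 | 96.9 v 96.8 |
| 4 (9.1%) | 30.2 v 29.8 | 30.6 v 29.0 | 31.9 v 29.2 |
| 5 (15.6%) | 50.7 v 50.3 | 51.2 v 50.0 | 51.6 v 49.9 |
| 6 (43.9%) | 92.5 v 92.7 | 91.8 v 92.0 | 90.8 v 91.4 |

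**Full six-parameter model**, separately coded, 1,800 trials per scenario. Scenario 8 gamma, outcome weights v SAP weights: −1.694 v −1.643 with two missing (0.051/1.694 = 3.0%) and −1.671 v −1.523 with six (0.148/1.671 = 8.9%). Complete-case gamma is −1.694 and −1.672, so the shrinkage comes from the weights and not from lost data. The efficacy decision changes in at least one cohort in 3.6% of trials with two missing and 12% with six. In Scenarios 5 and 9 gamma shrinks by 2.8–3.0% with two missing and 8.5–9.0% with six. This code's full-data approvals run 1.5 to 3.7 points above Table 6 in Scenario 1 and up to 2.6 points above in Scenario 9. The comparison of weightings uses the same draws and is unaffected.

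**Where it does not matter.** In Scenario 1 (no PD-L1 effect) posterior means agree within 0.001. Taking frequencies within pre-treatment group, which SAP 9.3.2 suggests differ, changes little: gamma −1.530 v −1.523 with six missing.

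**The case against.** The algebra is hard to dispute; the case against is about consequence.

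- **The shift is small.** It is about 0.06 posterior SD of gamma with two missing (0.051/0.88) and 0.16 with six. The regularising priors alone bias cohort 3 by −0.073 and cohort 4 by +0.031 with two missing; SAP weights make these −0.077 and +0.033.
- **Accuracy is a draw.** With six missing, RMSE in cohorts 1–6 is 0.082, 0.089, 0.155, 0.075, 0.083, 0.156 under SAP weights and 0.086, 0.092, 0.153, 0.074, 0.086, 0.154 under outcome weights. SAP pooling also had lower RMSE than complete-case analysis in every cohort.
- **Extra approvals are mostly right.** Cohorts 1, 2 and 5 truly exceed the hurdle; only cohort 4 does not, and its 9.1% is close to 10%.
- **Six and nine are assumed numbers.** The SAP limits the method to a modest amount of missing data.
- **The SAP model conditions on PD-L1** and gives it no distribution, so it has no posterior for a missing value until one is supplied. The fix also treats the frequencies as fixed.

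All of this stands as a limit on importance. The last point does not rescue the weights: step 3 itself supplies the covariate distribution, and once it does, the outcome term follows. Similar RMSE reflects extra shrinkage that happens to help some cohorts; it is not a property the plan chose or justified.

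**Conclusion.** The concern holds. Step 3 does not give the posterior implied by the SAP's efficacy model together with the PD-L1 frequencies it adopts. When PD-L1 predicts efficacy and is missing completely at random, High-cohort estimates fall and Low-cohort estimates rise. Across repeated simulations of Scenario 8, gamma is attenuated by 2.9–3.0% with two missing and 8.4–8.9% with six.

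The practical effect is modest. High-cohort approvals hardly move, while Low and Medium cohorts are approved slightly more often. The wrongful gain, in cohort 4, is 0.4–0.9 points with two missing and 1.6–3.2 with six, so the latter is known only to within a factor of two. These sizes rest on the assumed number missing, the missingness assumption and the SAP's scenario rates. The point should be corrected because it is an avoidable bias in a co-primary analysis rule; it does not threaten the trial's conclusions if few patients are affected.

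**What to change.** In step 3 of SAP 9.2.2.1, make each p_m proportional to the covariate frequency times the marginal likelihood of completed dataset m, then renormalise. Equivalently, in Stan give each patient with missing PD-L1 the likelihood sum_k rho_k · pi_ab(x_k, theta) over Low, Medium and High, in a single fit. Take rho_k within pre-treatment group; this is a minor refinement. Report the number with missing PD-L1 by pre-treatment status and outcome, and add a complete-case fit as a sensitivity analysis.

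The cost is one SAP paragraph and a few lines of code. SAP 11 says: "The Python implementation solves posterior integrals directly using Monte Carlo integration". The marginal likelihood is the normalising constant of those integrals. In Stan, the sum over categories replaces the separate fits.
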